## What is already known on this subject? AND What does this study add?

The use of Noninvasive Respiratory Support (NRS) as primary and post extubation respiratory support in Neonatal Intensive Care Unit (NICU) has increased in recent decades as a means to reduce ventilator-induced lung injury (*Mukerji and Dunn, 2016*).

The study evaluates the efficacy of Noninvasive High-Frequency Oscillatory Ventilation (NHFOV) and High Velocity Nasal Insufflation (Hi-VNI Vapotherm) in comparison to nasal CPAP as a primary noninvasive respiratory support in preterm infants. It also assesses echographic, cerebral blood flow and mesenteric blood flow changes during NHFOV and Hi-VNI Vapotherm in comparison to nasal CPAP.

## 1. INTRODUCTION

Respiratory distress is one of the most common causes of admission to NICU. Noninvasive ventilation (NIV) has significantly and positively altered the treatment outcomes and improved mortality rates of preterm infants with Respiratory Distress Syndrome (RDS) (*Permal et al., 2019*).

NIV can reduce the adverse effects associated with intubation and mechanical ventilation, such as bronchopulmonary dysplasia(BPD), sepsis, and trauma to the upper airways. In the last 4 decades, nasal CPAP has been used to wean preterm infants off mechanical ventilation and as a primary mode of respiratory support for preterm infants with respiratory insufficiency (*Mahmoud et al., 2011*).

Noninvasive high-frequency oscillatory ventilation (NHFOV) is a method of augmenting CPAP support in preterm infants, potentially combining the advantages of both invasive high-frequency oscillatory ventilation and CPAP (*De Luca and Dell'Orto, 2016*).

Vapotherm 2000i® is a noninvasive high-flow respiratory support system used mainly in the treatment of type 1 respiratory failure. It uses a mixture of oxygen and air to deliver a set concentration via nasal cannula. The advantage of this system is the high humidity achieved using the integral heated water system. The system has been used in neonatal practice as a replacement for nasal CPAP (*Price et al., 2008*).

Poor aeration of the lung leads to increased pulmonary vascular resistance and reduced blood flow. In contrast, overinflation of the lung causes compression of the vena cava, pulmonary vasculature, and heart. Low systemic blood flow and low superior vena cava (SVC) return are associated with increased morbidity in preterm infants. Therefore, the interaction between respiratory support and cardiac output (CO) is critically important (*Beker et al.,2014*).

## 2. AIM/ OBJECTIVES

1. Primary aim is to evaluate the efficacy of NHFOV and Hi-VNI Vapotherm in comparison to nasal CPAP as a primary noninvasive respiratory support in preterm neonates through assessment of:
  - The need for invasive mechanical ventilation (IMV) during the first 72 hours after enrollment in one of the groups, days of hospitalization, days on noninvasive respiratory support, days on supplemental oxygen, mortality, severe retinopathy of prematurity(ROP), air leak syndromes, intraventricular hemorrhage(IVH), necrotizing enterocolitis(NEC), nasal trauma and BPD.
2. Secondary aim is to assess haemodynamic changes during periods of non-invasive respiratory support including echocardiographic, cerebral blood flow and mesenteric blood flow changes.

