### 3. METHODOLOGY:

1. **Type of Study:** Randomized controlled trial.
2. **Study Setting:** NICU of Ain Shams University. Children hospital, Cairo, Egypt.
3. **Study Period:** Two years , from September 2021 till September 2023.
4. **Study Population:** Preterm neonates with RDS requiring noninvasive ventilation, the involved study group will be of matched gestational, postnatal age and sex.
5. **Inclusion Criteria:**
  - Preterm neonates with gestational age  $\leq$  35 weeks with RDS that need noninvasive ventilatory support primarily.
  - 6. Diagnosis of RDS is by clinical presentation, including signs of respiratory distress, ABGs showing hypoxemia and hypercapnia and chest x-ray showing diffuse atelectasis classically described as having a ground-glass appearance . (*Hermansen and Mahajan ,2015*).
  - 7. The need for noninvasive ventilation in the following situations :
    - Preterm with mild to moderate respiratory distress, Silverman score <6 (*Silverman and Anderson,1956*).
    - Mild to moderate hypoxemia (Fio2 less than 50% to maintain SpO2 (90%-94%)
    - Mild to moderate respiratory acidosis (PaCO2<65mmHg with pH>7.20)
    - Apnea (not associated with bradycardia, not needing bag and mask ventilation)
  - 8. **Exclusion Criteria:**
    1. Patients with major upper or lower airway anomalies.
    2. Patients with significant congenital anomalies including cardiac, abdominal or respiratory.
  - 9. **Sample size:** 90 participants
  - 10. **Sample size calculation:**

Sample size was calculated using One-way ANOVA F-test with significance level 0.05. Calculation according results from a previous study (*Abdelhady et al.,2008*) produced a sample size of 30 cases in each group.

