## 12. Study Procedures:

1. Detailed antenatal, natal and postnatal history. Gestational age will be estimated using the date of the last menstrual period and confirmed by the new Ballard scoring system (**Ballard et al., 1991**).
2. Full clinical examination including: chest, cardiac, abdominal, neurological examination and anthropometric measurements.
3. Patients' ages, mean arterial blood pressure, urinary output, temperature, capillary refilling time and O2 saturation by pulse oximetry and according, Oxygen Saturation Index (OSI) will be calculated as a noninvasive predictor of respiratory failure (**Muniraman et al., 2019**).
4. Daily inspection of infants' nostrils to evaluate the presence of skin alterations, nasal injury score will be used (**Khan et al., 2017**).
5. Surfactant if given with recording its timing and doses, Curosurf®; Chiesi pharmaceuticals, Parma, Italy. At a dose of 200 mg/kg will be administered via the INSURE method if an infant present with the following:
  - ≤30 weeks GA when FiO2 requirement >0.30 or >30 weeks GA when FiO2 requirement >0.40. In the INSURE technique, surfactant is administered via an endotracheal tube and after a brief period of positive pressure ventilation, patients will be extubated to the assigned mode. (**Zhu et al., 2018**).
6. Caffeine citrate; Chiesi Pharmaceuticals, Parma, Italy. Will be administered when infants present with significant apnea (defined as three or more episodes in 24 hrs or a single episode requiring resuscitation and bag and mask ventilation). The initial loading dose is 20 mg/kg, and the maintenance dose is 5 mg/kg per day (**Zhu et al., 2018**).
7. Assessment of feeding; method (parenteral or enteral) and detecting the type of milk, volume and duration to reach full enteral feeding together with recording presence of any feeding intolerance.
8. Recording of patients' days of hospitalization, days on noninvasive respiratory support, days on supplemental oxygen, initial settings and modifications, inotropic support, sepsis, incidence of ROP, air leak syndromes, IVH, NEC, BPD (**Jobe and Bancalari, 2001**) and mortality.

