### **C. Standard noninvasive mechanical ventilation group (CPAP):**

CPAP will be delivered by; MEDIN CNO device, medin Medical Innovations GmbH, Olching, Germany . Pressure ranging from 5 to 8 cm H2O,to maintain target oxygen saturation (SpO2) from 90% to 94%.

**We will define failure of non-invasive mode and need for invasive mechanical ventilation according to the following while on the maximum noninvasive settings :**

- Severe respiratory acidosis (PaCO2 ≥ 65 mmHg with pH ≤ 7.20),
- Severe apnea and bradycardia (defined as recurrent apnea with >3 episodes per hour associated with heart rate <100/min or a single episode of apnea that requires bag and mask ventilation)
- Hypoxemia (FiO2 >0.5 to maintain SpO2 90% to 94%)
- Severe respiratory distress characterised by retractions, moaning sounds or nasal flaring (defined as Silverman score >6) (*Silverman and Anderson, 1956*).
- Pulmonary haemorrhage and Cardiopulmonary arrest needing chest compressions (*Shi and De Luca, 2019*).

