### **14. Radiological investigation**

- A. Chest X-ray with radiological assessment of grades of RDS.
- B. Echocardiography : Two dimensional Echocardiography will be done using Vivid 9,GE Ultrasonography machine (Norway) with 6 MHz transducer frequency.To assess any structural cardiac anomalies, the patency of ductus arteriosus, right ventricular output (RVO), left ventricular output (LVO), and superior vena cava (SVC) flow.
- C. Transcranial ultrasonography by; Samsong Medison Co ,Korea. Doppler applied to the major cerebral arteries to provide an estimate of cerebral blood flow .
- D. Assessment of pre-prandial superior mesenteric artery (SMA) velocity and volume of blood flow with Doppler sonography by; Samsong Medison Co ,Korea.

**15. Statistical Analysis:** Numerical data will be summarized using mean and standard deviations or medians and inter quartile ranges. Qualitative data will be presented as count and percentage, p-value <0.05 will be considered significant.

**16. Statistical Package:** Statistical analysis will be performed with statistical package for social science (SPSS)

**17. Ethical Considerations:** A written informed consent will be taken from the parents or legal guardians before enrolment, after fully explaining to them the nature of the study. The approval of the Research Ethics Committee at Ain Shams University will also be obtained.

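### The primary aim lists 11 outcomes with no primary endpoint and no decision rule, so false-positive error on the main question is uncontrolled

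*Combined protocol and SAP*

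**What the plan says.** Section 2, item 1, reads "Primary aim is to evaluate the efficacy of NHFOV and Hi-VNI Vapotherm in comparison to nasal CPAP" and then gives, in one sentence, the outcomes through which this will be assessed. The first is need for invasive mechanical ventilation (IMV) in the first 72 hours. The list continues with "days of hospitalization, days on noninvasive respiratory support, days on supplemental oxygen, mortality, severe retinopathy of prematurity(ROP), air leak syndromes" and ends with IVH, NEC, nasal trauma and BPD. No outcome is ranked above another.

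Section 3, item 10 (sample size) says "Sample size was calculated using One-way ANOVA F-test with significance level 0.05". It names no outcome variable, effect size, standard deviation or power.

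Section 3, item 15 is the whole analysis plan: descriptive summaries and the statement that "p-value <0.05 will be considered significant". It names no test, hierarchy, multiplicity adjustment or rule for comparing two new modes with CPAP.

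Two parts of Section 3, item 12 bear on IMV as an endpoint. After the description of the CPAP group, the protocol says "We will define failure of non-invasive mode and need for invasive mechanical ventilation according to the following" and lists criteria. Point 5 describes surfactant given by INSURE, in which "after a brief period of positive pressure ventilation, patients will be extubated to the assigned mode".

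**The concern.** The 11 outcomes can disagree. A mode might reduce intubation but cause more nasal trauma, or shorten days on support because infants were intubated or died. The plan does not say which result decides efficacy, or whether one, several or all outcomes must be significant. That choice is left until the results are known.

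Nothing in the text prevents a single p-value below 0.05, on any of the 11, from being reported as evidence on the primary aim. The number of tests is also open. The ANOVA used for sample size hints at one three-arm test per outcome, while the aim to "evaluate the efficacy of NHFOV and Hi-VNI Vapotherm in comparison to nasal CPAP" allows two comparisons per outcome.

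**Working it through.** **Inputs from the documents.** Three arms of 30; 11 outcomes, of which 3 are durations (hospital, noninvasive support and oxygen days) and 8 are events (IMV within 72 h, mortality, severe ROP, air leak, IVH, NEC, nasal trauma, BPD); 0.05 per test.

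**The plan's own figure.** 3 × 30 = 90 agrees with the stated total. The 30 per group cannot be reproduced without an effect size or power. Working backwards with the noncentral F distribution (2 and 87 degrees of freedom, noncentrality 90f²), 30 per group gives 80% power at f = 0.333 and 90% at f = 0.382. Neither value is in the protocol, so the calculation does not reveal which outcome was intended as primary.

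**Closed form.** For 11 independent tests at 0.05, the chance of at least one false positive is 1 − 0.95¹¹ = 0.431.

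**Simulation under no treatment effect.** Assumptions not in the documents: event rates of 30, 20, 20, 15, 10, 10, 5 and 5%; equal correlation between outcomes; efficacy claimed if any one outcome reaches p < 0.05. There were 20,000 replicates with a shared CPAP arm. Chance of at least one false positive (%), by correlation:

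| Tests on the 11 outcomes | 0 | 0.3 | 0.5 | 0.7 | 0.9 |
|---|---|---|---|---|---|
| Three-arm: ANOVA, chi-square | 40.0 | 38.4 | 35.2 | 31.0 | 24.4 |
| Three-arm: ANOVA, exact test | 35.4 | 33.5 | 30.8 | 26.9 | 21.0 |
| Two CPAP comparisons: t, Fisher, either direction | 39.0 | 36.6 | 33.9 | 29.0 | 22.5 |
| Same, favouring a new mode only | 21.3 | 19.1 | 17.5 | 15.0 | 11.1 |

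With uncorrected chi-square for events, the two CPAP comparisons give 62.8% falling to 40.7% in either direction, and 38.1% falling to 20.8% favouring a new mode. Fisher's test gives lower figures because it is conservative at 30 per arm.

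**Other event rates.** Taking lower rates (3–20%) and higher rates (10–40%) together, the ranges become 19–42% for three-arm tests, 19–45% for t and Fisher in either direction, and 10–26% favouring a new mode.

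**Benchmarks for one outcome.**
- A single three-arm test has 5% error.
- Two unadjusted CPAP comparisons on one continuous outcome have 9.1% error in either direction and 4.6% favouring a new mode.
- On one binary outcome at 20–40%, two Fisher tests have 4.1–4.9% and 2.1–2.5%.

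**Error under a stated rule.** On one binary endpoint at 10–40%, by exact enumeration:
- Three-arm test, then comparisons with CPAP: 3.2–4.2% (chi-square) or 1.7–3.3% (exact).
- Holm across the two comparisons: 4.3–4.9% (chi-square) or 1.3–2.3% (Fisher).

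Either rule keeps error below 5%.

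**The case against.** The strongest reply is that IMV within 72 hours is the implied primary endpoint: it is listed first, is the only outcome with a time window, and has written criteria. But the protocol never designates it, and commas join it to ten others. The sample size does not point to it either. ANOVA suits a continuous variable, and the study cited as its basis is titled as one of haemodynamic changes during weaning from nasal CPAP, which is closer to the secondary aim. The title suggests this but does not prove it.

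A second reply is that error is undefined rather than inflated. If all 11 outcomes had to be significant, there would be no inflation. That is correct, and every percentage above is conditional on the any-one reading. No such requirement is written, however, and a plan that leaves the rule open does not control the error.

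Third, the sample-size ANOVA is weak evidence about the intended tests. That stands, which is why both three-arm and pairwise figures are shown.

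Fourth, INSURE intubation can be read as outside the failure definition, since that definition applies at maximum noninvasive settings and INSURE ends in extubation. This is a reasonable reading, but the protocol does not state it.

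Finally, a choice of endpoint made now may be post hoc. That limits what the change can achieve, but it makes disclosure more important.

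**Conclusion.** The concern holds and must be fixed. The absence of a primary endpoint and a decision rule is plain from the text and does not depend on any simulation.

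Its size does depend on assumptions. If any one significant outcome counts as efficacy, the false-positive chance is about 21–40% with three-arm tests and 23–39% with two CPAP comparisons by t and Fisher tests, of which 11–21% is error favouring a new mode. Uncorrected chi-square raises the pairwise figure to 41–63%. Event rates, correlations and the any-one rule are all assumed. Every scenario for the 11 outcomes exceeds the benchmark for a single outcome tested in the same way.

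**What to change.** 1. **Name one primary endpoint.** Need for IMV within 72 hours is the natural choice, though the decision is the sponsor's.
2. **Settle its definition first.** Item 12 gives surfactant at FiO2 above 0.30 or 0.40, depending on gestational age, while failure requires FiO2 above 0.5. An infant can therefore be intubated for INSURE without meeting a failure criterion. The two passages must be reconciled on whether that intubation counts as IMV.
3. **State one rule for the two CPAP comparisons.** Use either a three-arm test at 0.05 followed by comparisons with CPAP, or Holm across the two comparisons.
4. **Make the other ten outcomes secondary.** Report estimates with 95% confidence intervals, and draw no efficacy claim from individual p-values.
5. **State the precision that 30 per arm gives** for the chosen endpoint. No further enrolment is proposed.
6. **Disclose timing.** The study period runs "from September 2021 till September 2023". If outcome data have already been examined, describe the choice as post hoc.

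The cost is a few sentences, with no extra infants or measurements. There are three drawbacks:
- Efficacy can no longer be claimed from the other ten outcomes.
- Low power becomes visible. At an assumed 40% on CPAP against 20% on a new mode, the interval half-width is 1.96 × √(0.24/30 + 0.16/30) = 0.226, about 23 percentage points. One unadjusted comparison has 39% power by chi-square or 30% by Fisher's test. For a given mode, the three-arm-then-pairwise rule has 31–32% (chi-square) or 26% (exact), and Holm has 30–33% or 20–22%. These powers describe one assumed scenario only.
- A late choice carries less weight than a prespecified one.

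### The plan has no rule for infants who die in the analysis of hospital, oxygen and NRS days, BPD and severe ROP, so an arm with more deaths can look better.

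*Combined protocol and SAP*

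**What the plan says.** Section 2 (Aim/Objectives), item 1, gives eleven outcomes under the primary aim. Five matter here: "days of hospitalization, days on noninvasive respiratory support, days on supplemental oxygen, mortality, severe retinopathy of prematurity(ROP" (leaving mortality aside, that is three durations and severe ROP), and BPD at the end of the list: "necrotizing enterocolitis(NEC), nasal trauma and BPD". Mortality and need for invasive mechanical ventilation (IMV) within 72 hours are separate items in the same list. BPD and severe ROP are not combined with death.

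Section 12 (Study Procedures), item 8, says what is recorded: "days on noninvasive respiratory support, days on supplemental oxygen, initial settings and modifications", and "incidence of ROP, air leak syndromes, IVH, NEC, BPD". It gives no rule for deaths, no denominator and no assessment age. A source is cited for BPD. For ROP no grade is given.

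The analysis text is item 15 (Statistical Analysis): "Numerical data will be summarized using mean and standard deviations or medians and inter quartile ranges", and "Qualitative data will be presented as count and percentage", with significance at p<0.05. It names no analysis population.

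On noninvasive respiratory support (NRS), item 5 of Study Procedures says that after INSURE "patients will be extubated to the assigned mode". The text following the CPAP group begins "We will define failure of non-invasive mode and need for invasive mechanical ventilation" and lists the criteria. Neither place says how NRS days are counted afterwards.

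**The concern.** Death stops the clock on a stay in hospital, on oxygen or on NRS, and it prevents a later diagnosis of BPD or severe ROP. For each of these five outcomes a low value is meant to indicate efficacy. If every randomised infant enters the summary at face value, an early death contributes a favourable value, and the bias runs towards the arm with more deaths.

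Restricting to survivors is neither planned nor excluded. It conditions on something that happens after randomisation, and it too is biased if the sicker infants die. The choice matters and should not be made after the data are seen.

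NRS days carry a second, smaller ambiguity: whether the count stops at failure or resumes after a later extubation.

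**Working it through.** **No plan figure to reproduce.** The plan gives no mortality, duration, failure, BPD or ROP rates. Its one number, 30 per group (Methodology, items 9 and 10), comes without power, effect size or SD, so it cannot be reproduced, and this point does not rest on it. Apart from 30 per arm, every input below is assumed.

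**Step 1, by hand.** 30 per arm; 3 vs 6 deaths on day 5; survivors identical (30-day stay, one third with BPD).

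| | 3 deaths | 6 deaths |
|---|---|---|
| Mean stay, all infants | (27×30 + 3×5)/30 = 27.5 d | (24×30 + 6×5)/30 = 25.0 d |
| BPD, all randomised | 9/30 = 30.0% | 8/30 = 26.7% |
| BPD, survivors | 9/27 = 33.3% | 8/24 = 33.3% |
| BPD or death | 12/30 = 40.0% | 14/30 = 46.7% |

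The first two rows favour the arm with more deaths. The last reverses the order.

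**Step 2, hospital days.** Survivors: gamma, mean 35 d, SD 10, 15 or 20. Deaths: uniform on days 0.5–14 (mean 7.25). With deaths at random, the mean at mortality m is 35(1−m) + 7.25m. At m = 5% this is 33.6 d; at 10%, 15% and 20% it is 32.2, 30.8 and 29.5 d. Simulated trials of 30 vs 30, two-sided Mann-Whitney at 0.05, counting only significant results that favour the arm with more deaths (about 2.5% by chance):

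| Mortality | Deaths at random | Deaths only in the half with longer latent stay |
|---|---|---|
| 5% vs 10% | about 5% | about 7% |
| 5% vs 15% | 8–9% | 15–17% |
| 5% vs 20% | 14–16% | 29–33% |

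With three arms (5%, 15%, 5%) and a Kruskal-Wallis test first, the 5% vs 15% figures fall to 5–6% and 10–12%.

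Survivors only, 5% vs 15%: 35.0 vs 35.0 d if death is unrelated to severity; 34.2–34.6 vs 32.3–33.6 d, with about 6% in the wrong direction, if it is related.

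Deaths ranked worst, 5% vs 15%: wrong direction about 0.3–1.6% over both patterns of death. The worse arm is detected in only about 5–10% of trials.

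**Step 3, oxygen days.** Survivors: gamma, mean 12 d, SD 6, 8 or 10; same deaths, at random. At 5%: 12×0.95 + 7.25×0.05 = 11.8 d. At 15%: 12×0.85 + 7.25×0.15 = 11.3 d. Wrong direction 3.5–4.5%, close to chance. Confining deaths to infants with longer latent oxygen need about doubles this in the same simulation.

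**Step 4, BPD or severe ROP.** Underlying risk 20% in both arms, 50% in infants who die. Expected diagnosed cases are 30(0.20 − 0.5m): 5.3 at 5% mortality, 3.8 at 15%. Event-or-death is 30(0.20 + 0.5m): 6.8 and 8.3.

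**Step 5, NRS days.** Mean 6 d without failure; failure at 0.1–2 d (mean 1.05); failure in 10% vs 30%; L later NRS days after failure. Mean = 6(1−f) + (1.05 + L)f.

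| L | 10% failure | 30% failure | Significantly favours more failure |
|---|---|---|---|
| 0 | 5.5 d | 4.5 d | 25% |
| 3 | 5.8 d | 5.4 d | 8% |
| 6 | 6.1 d | 6.3 d | 1% |

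The order depends on how much later NRS is given and counted.

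**Step 6, is mortality a safeguard?** Exact Fisher power for 5% vs 15% mortality with 30 per arm is 9.3%.

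**The case against.** Mortality and IMV are in the same list, so excess deaths would be visible. That stands and helps a careful reader. But at 30 per arm a threefold difference in mortality would usually be non-significant, and nothing links it to the duration or morbidity comparisons.

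Every size is assumed. Entry is limited to mild-to-moderate disease, and the documents support no particular mortality contrast. The larger figures need a three- or fourfold ratio, some with deaths confined to infants with longer stays. The Mann-Whitney test is not named in the plan, and a three-arm test shrinks the effect. All of this stands: the effect is reduced but not removed.

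Three stronger readings are tempting. A reader might infer that the plan scores deaths as short stays. It does not say so; it is silent, and the bias follows only if all infants are summarised as recorded. A reader might infer that failure of the assigned mode shortens NRS days and so flatters the failing arm. The wording refers to noninvasive support in general, not to the assigned mode, so its plain reading counts later NRS days too. The 25% figure arises only if no later NRS is given or counted, so this part is mainly a matter of definition. A reader might also infer that support-free days to day 28 are the necessary remedy. They are not, and they need data that the plan does not list.

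**Conclusion.** The concern holds in this form. Five of the eleven primary-aim outcomes have no rule for death. Summarised over all infants, they lean towards the arm with more deaths, so this is a potential bias and not only missing wording. For hospital days the effect is modest: about 8–9% wrong-direction significance, or 15–17% if sicker infants die, at an assumed 5% vs 15% mortality, and less behind a three-arm test. For oxygen days it is close to chance with deaths at random. For BPD and severe ROP it is about 1.5 expected cases per 30 under the stated assumptions (5.3 − 3.8). For NRS days the direction cannot be settled until the count is defined. The plan should be changed. Confidence is medium, because the omission is plain but no rate comes from the documents.

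**What to change.** 1. Compare hospital days and oxygen days with deaths ranked as the worst outcome, using a rank test named in advance. This needs only the date of death or discharge.
2. Analyse BPD as BPD or death before BPD assessment, and severe ROP as severe ROP or death before ROP assessment, over all randomised infants. State the assessment age for each and show the components separately.
3. Count NRS days as all days on any noninvasive support, including after INSURE and after a failed-mode intubation. Rank deaths worst, and read the result beside IMV.
4. Keep plain day counts, or survivors-only summaries, as description beside mortality.

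Days alive and free of support or oxygen to day 28 is optional. It needs start and stop dates and days on invasive ventilation, which Study Procedures item 8 does not list. Under the assumed stay, 26%, 36% or 43% of survivors (SD 10, 15 or 20) leave before day 28. Their status would need post-discharge contact, or a stated assumption that they are alive and support-free.

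Items 1 to 4 cost analysis-plan wording, the dates and the assessment ages. The downsides are less familiar measures, little added power, and composites that mortality may drive: in Step 4 the event-or-death difference comes entirely from mortality, which is why the components must be shown.
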